#### 14.1.1.1. Derivations

Based on the aforementioned immunogenicity variables, the following variables, as presented in the planned TLF shells, will be derived:

- Log-transformed concentration values:
  - o Log10 of the concentration values will be derived.
  - o Results below the cut-off of the assay will be assigned as half of the cut-off\* value before taking the log for analysis purposes.
- Serological status:
  - o Seronegative:  
Concentration value is below the cut-off\* value.
  - o Seropositive:  
Concentration value is greater or equal to the cut-off\* value.
  - o Seroconversion:  
Seropositive result post-vaccination for any subjects defined as seronegative pre-vaccination.
- Response:
  - o Yes:  
For seronegative pre-vaccination: Post-vaccination concentration value of at least the assay cutoff value.  
For seropositive pre-vaccination: Post-vaccination concentration value of at least x-fold increase over the pre-vaccination concentration value.
  - o No:  
For seronegative pre-vaccination: Post-vaccination concentration value of less than the assay cutoff value.  
For seropositive pre-vaccination: Post-vaccination concentration value of less than x-fold increase over the pre-vaccination concentration value.

The x-fold increase will be calculated as:

$$= \frac{\text{Post-vaccination concentration value}}{\text{Pre-vaccination concentration value}}$$

Document: CHAD3-004-EBO-Z\_Interim\_Final\_SAP\_v2\_0

Author: PPD Version Number: 2.0 Version Date: 14JUN2017

Template No: CS\_TP\_BS016 – Revision 3

Reference: CS\_WI\_BS005

Effective Date: 01May2012

NOTE: Assay cut-off value is defined as 36.11 EU/mL.

NOTE: x-fold is defined as 3-fold.

#### 14.1.2. CHAd3 NEUTRALISING ANTIBODY

All analyses will be the same as described for the anti-GP EBOV data. The same tables as described for the antiGP EBOV data will be prepared for the ChAd3 neutralisation data. The ChAd3 neutralisation result will be the reciprocal antibody titres corresponding to the inhibitory concentration 90% (IC90, the titre at which 90% of infectivity is inhibited).

In addition, the association of the pre-existing (baseline) ChAd3 neutralisation antibodies with each of the following vaccine-induced (Day 30 post-vaccination) results will be evaluated by the Spearman-rank correlation method:

- Anti-GP EBOV: Concentration.
- Frequency of CD4+ T-cell specific to EBOV:
  - o CD4+/IFN. o  
CD4+/I  
L2.
  - o CD4+/TNF.
- Frequency of CD8+ T-cell specific to EBOV:
  - o CD8+/IFN. o  
CD8+/I  
L2. o  
CD8+/T  
NF.

Three scatter plots will be presented per cytokine (IFN, IL2, TNF), one plot for each of the aforementioned sets of results. The vaccine-induced results will be based on the result observed at Day 30. The figure will be repeated for the 30 Days Post-vaccination derived time point as defined in Section 6.3.1: ChAd3-EBO-Z Post-vaccination Time Points.

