### 2.2.2. SECONDARY ENDPOINT

- Anti-GP EBOV antibody concentrations, as measured by enzyme-linked immunosorbent assay (ELISA):
  - o At Day 0 and Day 30, in all subjects, in both groups.
  - o At Month 6 and Month 6 + 30 days, in all subjects in the Group MENACWY-TT/EBO-Z.

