## 7. STATISTICAL CONSIDERATIONS

### 7.1. ADJUSTMENTS FOR COVARIATES AND FACTORS TO BE INCLUDED IN ANALYSES

Not applicable.

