## 14.1. HUMORAL IMMUNE RESPONSE

### 14.1.1. ANTI-GLYCOPROTEIN (GP) EBOLA VIRUS ZAIRES (EBOV)

The following listing is planned for presentation for the Total Vaccinated Cohort: Immunogenicity:

- Anti-GP EBOV results.

The following tables are planned for presentation for the According-to-protocol Cohort:

- Anti-GP EBOV: Serological status:
  - o The number and percentage (%) of subjects in each status category (seronegative, seropositive and seroconversion for post-vaccination time points).
  - o Percentage (%) calculated relative to the number of subjects with results available in order to assign a status at each time point.
  - o 95% CIs for the seropositivity and -negativity rates will be presented for each treatment group.
- Anti-GP EBOV: Response:
  - o The number and percentage (%) of subjects in each category (Yes and No).
  - o Percentage (%) calculated relative to the number of subjects with results available at both pre-and post-vaccination time points at each time point.
  - o 95% CIs for the response rate will be presented for each treatment group.
- Anti-GP EBOV: Geometric mean concentrations (GMC) (depending on the outcome of validation):
  - o Summary statistics, refer to Section 6.6: Statistical Tests, based on the log-transformed concentration values.

---

Document: CHAD3-004-EBO-Z\_Interim\_Final\_SAP\_v2\_0  
Author: PPD Version Number: 2.0 Version Date: 14JUN2017

Template No: CS\_TP\_BS016 – Revision 3  
Effective Date: 01May2012

Reference: CS\_WI\_BS005

- o 95% CIs will be presented for the GMCs per each treatment group.
- o GMC calculations are performed by taking the anti-log of the mean of the log10 concentration transformation.
- Anti-GP EBOV: Day 0 Geometric Mean Concentration
  - o Summary statistics, refer to Section 6.6: Statistical Tests, based on the log-transformed concentration values.
  - o This outputs would only contain the Baseline seropositive subjects.
  - o Only Day 0 results will be presented. o 95% CIs for the GMCs will be presented for each treatment group.
  - o GMC calculations are performed by taking the anti-log of the mean of the log10 concentration transformation.

The following figures are planned for presentation for the According-to-protocol Cohort:

- Reverse cumulative distribution curves:
  - o Each plot shows antibody concentrations (on a log-scale) on the X-axis and the proportion of individuals exhibiting that concentrations or higher on the Y-axis.

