- Day 0 Reverse Cumulative Distribution curve:
  - o The plot shows antibody concentrations (on a log-scale) on the X-axis and the proportion of individuals exhibiting that concentrations or higher on the Y-axis.
  - o This output would only contain the Baseline seropositive subjects. o Only Day 0 results will be presented.
- Concentration and GMCs:
  - o Individual antibody concentrations at Day 0 and Day 30, with dot plots, per treatment group. o GMCs and 95% confidence intervals will also be plotted.
- Kinetic plot (only applicable to the final analysis):
  - o GMCs, including 95% CIs at the EBO-Z post-vaccination time points. o Time points will be connected with straight lines.

All anti-GP EBOV tables will be presented by Baseline serological status, including the following categories:

- Seronegative.
- Seropositive.
- Total.

The following immunology variables, as presented in the planned TLF shells, will be collected on the Blood Sampling form in eSource:

- Were humoral immunity blood samples collected:
  - o Y

---

Document: CHAD3-004-EBO-Z\_Interim\_Final\_SAP\_v2\_0

Author: PPD Version Number: 2.0 Version Date: 14JUN2017

Template No: CS\_TP\_BS016 – Revision 3

Reference: CS\_WI\_BS005

Effective Date: 01May2012

es. o

No.

- Date and time of sample collection.

The following immunology variable, as presented in the planned TLF shells, will be imported from the laboratory report:

- Concentration value.

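### The planned correlation of baseline ChAd3 antibody with Day 30 anti-GP ignores each child's pre-vaccination anti-GP value, so it can be biased in a direction and by an amount that the documents do not fix

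*SAP*

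**What the plan says.** SAP v2.0 section 14.1.2 takes "the association of the pre-existing (baseline) ChAd3 neutralisation antibodies" as one variable and the Ebola-specific results as the other: the "vaccine-induced (Day 30 post-vaccination) results will be evaluated by the Spearman-rank correlation method". It defines the second plainly: "The vaccine-induced results will be based on the result observed at Day 30". For anti-GP EBOV the listed variable is the concentration. No change from Day 0, fold-rise, partial correlation or restriction to seronegative children is mentioned, and section 7.1 on covariates reads not applicable. For the pooled data, "The figure will be repeated for the 30 Days Post-vaccination derived time point".

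Elsewhere the plan does use the pre-vaccination value. Section 14.1.1 says "All anti-GP EBOV tables will be presented by Baseline serological status", and section 14.1.1.1 requires a 3-fold rise before a seropositive child counts as a responder. Section 14.1.1 also plans a Day 0 geometric mean concentration table, of which it says "This outputs would only contain the Baseline seropositive subjects", so seropositive children were expected. The split by baseline status is stated for tables, whereas the correlation is introduced separately and shown as scatter plots.

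The value needed is collected. Section 2.2.2 has anti-GP measured "At Day 0 and Day 30, in all subjects, in both groups", and at Month 6 in the MENACWY-TT/EBO-Z group.

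**The concern.** The tertiary objective (Protocol section 2.3) is to explore whether pre-existing immunity to the vector affects the Ebola-specific response. Section 14.1.2 is the only specified analysis that relates the two. The natural question is whether children with more ChAd3 antibody mount a smaller response to the vaccine. In a child who already reads above the assay cut-off, the Day 30 concentration reflects the vaccine response together with whatever was there before. Calling it vaccine-induced attributes all of it to the vaccine.

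This matters for the coefficient if pre-vaccination anti-GP is related to ChAd3 titre. A positive relation raises Day 30 values in the children whose response is expected to be blunted, and makes blunting look weaker. A negative relation makes it look stronger. The subset is small enough for a modest shift to change how the result is read.

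**Working it through.** **Size of the analysis.** Protocol section 5.2.3 gives about 30 children per stratum per group: 30 x 3 = 90 per group, and 90 x 2 = 180 in total, as stated there. No expected coefficient, confidence level or power is given for this correlation.

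**Precision at that size.** Fisher z with SE = 1.06/sqrt(n - 3), for an illustrative Spearman coefficient of -0.30 (z = -0.310):

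- n = 90: SE = 1.06/sqrt(87) = 0.114; the 95% interval on z is -0.532 to -0.087, which is -0.49 to -0.09 as a correlation.
- n = 30 (one stratum): SE = 1.06/sqrt(27) = 0.204; the interval is -0.61 to +0.09.

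**Direction of the bias.** Let r1 be the rank correlation of ChAd3 titre with pre-vaccination anti-GP, and r2 that of pre-vaccination anti-GP with Day 30 anti-GP. The partial coefficient is

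partial = (raw - r1 x r2) / sqrt[(1 - r1^2)(1 - r2^2)],

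so raw = partial x sqrt[(1 - r1^2)(1 - r2^2)] + r1 x r2. Where pre-existing signal carries through, r2 is positive. The added term then has the sign of r1: upwards, against a negative effect, if r1 is positive, and downwards if r1 is negative. If r1 is zero, only the shrinkage from r2 remains.

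**Simulation 1 (every input assumed).** True coefficient -0.30; 40% of ChAd3 titres below cut-off; vaccine-induced median 500 EU/mL, log10 SD 0.45; n = 90, 3,000 replicates. Seronegative children receive half the cut-off, 36.11/2 = 18.055 EU/mL (SAP section 14.1.1.1). With 20% seropositive at a median of 200 EU/mL:

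| Carry-over to Day 30 | Coefficient | Link 0 | Link 0.3 | Link 0.5 |
|---|---|---|---|---|
| Additive | raw | -0.28 | -0.24 | -0.21 |
| Additive | partial | -0.29 | -0.28 | -0.28 |
| Proportional | raw | -0.25 | -0.15 | -0.08 |
| Proportional | partial | -0.29 | -0.28 | -0.27 |

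The link is the assumed correlation between the two baselines. Limits of this set:

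- No seropositive children: raw and partial are both -0.30.
- Mildest case (10% seropositive, median 72 EU/mL, additive, no link): both -0.29.
- No link but heavy carry-over (50%, 200 EU/mL, proportional): raw -0.21, partial -0.29.
- Strongest case (50%, 200 EU/mL, proportional, link 0.5): raw +0.02, partial -0.27.

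**Simulation 2 (every input assumed, negative links included).** True coefficient -0.34; 10 to 40% seropositive; Day 0 medians in seropositive children of 60 to 200 EU/mL; vaccine-induced geometric mean 160 or 500 EU/mL, log10 SD 0.4; link -0.3 to +0.5; additive carry-over. Raw runs from about 0 to -0.40 and partial from -0.28 to -0.34; seronegative children alone give -0.32 to -0.34. With 20% seropositive and a link of -0.3, raw is -0.35 to -0.38, so blunting is overstated.

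**Fold-rise.** In the Simulation 1 cases with seropositive children, the fold-rise coefficient ran from -0.18 to -0.43 against a true -0.30, because all seronegative children share one imputed denominator. It is not a clean substitute.

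**The case against.** The strongest reply is that no document supplies the input that creates the harm. Neither the share of children seropositive before vaccination nor the sign or size of the link with ChAd3 titre is given. The trial is planned in areas free of Ebola transmission, and known prior disease is an exclusion, so how far a low pre-vaccination reading adds to the Day 30 value is also unknown. All of this stands. A reader might infer that the planned coefficient will hide blunting by vector immunity. The documents do not support that: a negative link overstates blunting, and with no link the bias is small unless carry-over is heavy.

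A reader might also infer that the problem is separate from age and equally present within one stratum. That is not shown. The simulations contain no age, and if both baselines rise with age, the link would shrink within a stratum.

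Second, the definition is open, Day 30 concentration is itself a secondary endpoint, and correlating it is legitimate. That stands as a reason to keep the raw coefficient, but not for the label.

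Third, related outputs already exist: tables split by serostatus, individual Day 0 and Day 30 plots, and a baseline-aware response rule. If the correlation is shown by group, MENACWY-TT/EBO-Z at Day 30 would show background association before any ChAd3-EBO-Z. None of these outputs corrects the coefficient, and the SAP does not name the last as a check. The table and figure shells are not available, so whether the scatter plots mark serostatus is unknown.

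Finally, the partial coefficient is not exactly unbiased (-0.28 at worst against -0.34), since most Day 0 values may be tied at the imputed value. It is nevertheless closer than raw wherever the raw bias is material.

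**Conclusion.** The point holds as a limited one. Section 14.1.2 labels an unadjusted Day 30 level as vaccine-induced and leaves out a pre-vaccination value that the plan collects and uses elsewhere. If some children are seropositive before ChAd3-EBO-Z, the coefficient can be biased either way. With an assumed true value of -0.34, raw lies anywhere from about 0 to -0.40. That is a range over assumptions, not an estimate for this trial, and no single scenario in it should be quoted as the expected loss. With no seropositive children there is no bias.

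The consequence is confined to a tertiary question. SAP section 7.4 says that all analyses are descriptive, and no primary or secondary conclusion depends on this coefficient. It is worth correcting because the correction needs no new data, not because harm has been shown.

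**What to change.** In SAP section 14.1.2, for the anti-GP EBOV correlation:

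1. Add a partial Spearman coefficient between baseline ChAd3 titre and the Day 30 concentration, adjusted for the last anti-GP value before ChAd3-EBO-Z. Name that value: Day 0 in EBO-Z/MENACWY-TT and, for the pooled repeat, Month 6 in MENACWY-TT/EBO-Z. Naming it matters because section 6.2 ties baseline to the first vaccination, about six months before ChAd3-EBO-Z in the second group.
2. Add the Spearman coefficient in children who are seronegative at that same time point.
3. Keep the raw coefficient and its scatter plot, but label the outcome *Day 30 level* and not *vaccine-induced*.
4. Do not use fold-rise as the only alternative.

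The cost is a short change of SAP wording and a few lines of code. All values are already planned for collection.

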**2.3. Tertiary objectives**

[figure not shown]
- To assess the persistence of the humoral immune response induced by a single IM dose of the ChAd3-EBO-Z vaccine, in terms of anti-GP EBOV antibody responses, overall and in children aged 1 to 5, 6 to 12, and 13 to 17 years separately.
- To assess EBOV specific cell-mediated immunity (CMI) of a single IM dose of the ChAd3-EBO-Z vaccine, overall and in children aged 1 to 5, 6 to 12, and 13 to 17 years separately.
- To assess the pre-existing immunity to the ChAd3 virus vaccine vector prior vaccination, ChAd3-specific immune responses after vaccination and explore its potential impact on Ebola-specific immune responses, overall and in children aged 1 to 5, 6 to 12, and 13 to 17 years separately.
- If deemed necessary, to further characterise the immune response to/ the safety profile of the investigational ChAd3-EBO-Z vaccine.

Refer to [Section 11.3](#) for the definition of the tertiary endpoints.

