### **11.9. Analysis of immunogenicity**

The primary analysis will be based on the ATP cohort for analysis of immunogenicity. If, in any study group, the percentage of vaccinated subjects with serological results excluded from the ATP cohort for analysis of immunogenicity is 5% or more, a second analysis based on the TVC will be performed to complement the ATP analysis.

All analyses will be descriptive. Analyses will be performed by age stratum (1 to 5 years, 6 to 12 years, 13 to 17 years) and overall.

In a first step, the immunogenicity results will be presented by treatment administered at Day 0 (ChAd3-EBO-Z vaccine [300 subjects] versus *Nimenrix* [300 subjects]). In a second step, all data post-vaccination with the investigational ChAd3-EBO-Z vaccine (ChAd3-EBO-Z vaccine at Day 0 [300 subjects] and ChAd3-EBO-Z vaccine at Month 6 [300 subjects]) will be pooled (600 subjects). The latter aggregated data cannot be presented versus control because of the administration of the investigational ChAd3-EBO-Z vaccine to the children in the Group MENACWY-TT/ EBO-Z, who initially received *Nimenrix* (population overlap).

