### 7.5. EXAMINATION OF SUBGROUPS

No subgroup analyses will be performed for this study.

Document: CHAD3-004-EBO-Z\_Interim\_Final\_SAP\_v2\_0  
Author: PPD Version Number: 2.0 Version Date: 14JUN2017

Template No: CS\_TP\_BS016 – Revision 3  
Effective Date: 01May2012

Reference: CS\_WI\_BS005

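### The overall Spearman coefficient for pre-existing ChAd3 antibody should be stratified by, or partial on, age, because it is biased if baseline titre and Day 30 response both vary with age

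*SAP*

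**What the plan says.** SAP v2.0 section 14.1.2 relates pre-existing ChAd3 neutralising antibody to seven later results: anti-GP concentration, and CD4+ and CD8+ frequencies for each of IFN, IL2 and TNF. Each association "will be evaluated by the Spearman-rank correlation method". On timing, "The vaccine-induced results will be based on the result observed at Day 30", with the figure repeated at the derived time point 30 days after ChAd3-EBO-Z. The section does not mention age.

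SAP 7.1, on covariates, reads "Not applicable". SAP 7.5 reads "No subgroup analyses will be performed for this study".

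The protocol goes further. Its section 2.3 asks for the "potential impact on Ebola-specific immune responses, overall and in children aged 1 to 5, 6 to 12, and 13 to 17 years separately", and SAP 2.3.1 repeats the same strata. Protocol 11.9 sets the general rule for immunogenicity: "Analyses will be performed by age stratum (1 to 5 years, 6 to 12 years, 13 to 17 years) and overall". SAP 3.3 declares no change from the protocol.

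The ChAd3 assay is run in the CMI sub-cohort, about 30 children per age stratum per group (SAP 5.5.1 and 5.5.2).

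**The concern.** The sub-cohort is recruited in three equal age blocks, so it has a wide spread of age by design. If baseline ChAd3 titre rises or falls with age, and the response to the vaccine does too, a crude rank correlation over ages 1 to 17 picks up the shared dependence on age. It can then be non-zero although vector immunity has no effect at a given age. If the two gradients run in the same direction, it can hide a real negative effect.

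One route to a response gradient is in the documents themselves. Protocol 1.2.2.1 and Tables 14 and 15 allow a lower ChAd3-EBO-Z dose in the younger strata. If that option were used, dose would change with age stratum, and an unadjusted coefficient would absorb it.

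At stake is the reading of one tertiary objective. The overall figure is the one a reader is likely to take away, because it rests on three times as many children as any single stratum.

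**Working it through.** **Inputs.** From the SAP: 30 per stratum per group. Check: 30 × 3 = 90 per group and 90 × 2 = 180 in total, which matches SAP 5.5.1. Assumed, because the documents give neither: the correlation of baseline titre with age (a) and of Day 30 response with age (b). Also assumed: ages uniform within each stratum, and normal variables. The documents state no target coefficient, alpha or power for this analysis.

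**Crude coefficient with no link at a given age.** The correlation induced by age is approximately a × b.
- a = 0.3, b = -0.3: -0.09
- a = 0.4, b = -0.4: -0.16
- a = 0.5, b = -0.5: -0.25
- a = 0.5, b = 0: 0

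**What stratification leaves.** Treat the strata as age ranges 1 to 6, 6 to 13 and 13 to 18 in continuous years. The within-stratum variance of age is (25 + 49 + 25)/36 = 2.75. The stratum means are 3.5, 9.5 and 15.5, so the between-stratum variance is (36 + 0 + 36)/3 = 24. The share of age variance left within strata is w = 2.75/26.75 = 0.103. With |a| = |b|, the residual is w·ab / [(1 − a²) + w·a²].
- 0.3: -0.0093/0.919 = -0.010
- 0.5: -0.0257/0.776 = -0.033

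**Simulation, n = 90, no true link at a given age** (1,500 runs per row):

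| a, b | Crude Spearman | Mean of within-stratum Spearman | Partial Spearman on age |
|---|---|---|---|
| 0.3, -0.3 | -0.09 | -0.01 | 0.00 |
| 0.4, -0.4 | -0.16 | -0.02 | 0.00 |
| 0.5, -0.5 | -0.25 | -0.03 | 0.00 |
| 0.5, 0 | 0.00 | 0.00 | 0.00 |

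The simulated values agree with the formulas. At n = 180 (both groups pooled after ChAd3-EBO-Z) the mean crude coefficient is the same, -0.25 in the 0.5 case. More children shrink the sampling error but not the bias.

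**Ties.** Protocol 1.1.3 reports low ChAd3 seroprevalence, so many baseline titres may share the value given to results below the cut-off of 12. With 70% tied (assumed), the 0.5 case falls to -0.20.

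**Masking.** Take a true correlation of -0.3 at a given age and both gradients at +0.5. The crude value is approximately 0.25 + (-0.3)(0.75) = 0.025. Simulation gives +0.04 crude, against -0.24 with within-stratum ranks.

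**Precision of a single stratum.** With n = 30, the coefficient that reaches a nominal two-sided 5% is tanh(1.96/√(27/1.06)) = 0.37. With n = 90 it is 0.21. The three stratum values will therefore be imprecise when read alone.

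**The case against.** The strongest reply is that the plan already contains the remedy. Protocol 11.9 and the objective itself call for results in each stratum, and SAP 3.3 declares no departure from the protocol. SAP 7.5 is hard to read as cancelling the strata, because the same SAP lists stratum-specific objectives and presents pooled adverse-event tables per age stratum (15.1.2). Layout is left to the table shells, which are not among the documents. A reader who sees three near-zero stratum values beside a pooled one is partly protected. This stands. One might infer from 14.1.2 that a single all-ages correlation is the whole analysis, and the documents do not support that.

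The second reply is that the age gradients are unsupported. No passage reports how ChAd3 titre or anti-GP response varies with age, and the low seroprevalence reported for this vector points to weaker correlations. This also stands. It makes the bias conditional, and it rules out any statement that the coefficient will be wrong.

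The third reply is that SAP 7.4 describes every analysis as descriptive and no test is specified for this correlation. In the simulation the crude coefficient passes a nominal two-sided 5% level in 11% of runs at gradients of 0.3, and in 67% at 0.5. It is tempting to read those as error rates of the trial, but the plan makes no such test.

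None of these replies covers the overall coefficient. The objective requires it, and section 14.1.2 provides no way of computing it free of age.

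**Conclusion.** The point holds in a limited form. The overall Spearman coefficient is unadjusted and would be confounded if both baseline titre and Day 30 response depend on age. Under assumed opposite gradients of 0.3 to 0.5 and no true link, the crude coefficient is off by about 0.09 to 0.25, against 0.01 to 0.03 within strata. The bias is nil if only one measure varies with age, and smaller if many titres are tied. Same-direction gradients would give a false positive association or mask a negative one.

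The consequence is a misleading descriptive figure on a tertiary objective. No primary or secondary conclusion depends on it.

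Separately, SAP 7.5 and protocol 11.9 do not agree on their face about results by age stratum.

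Whether the Day 30 version should be limited to ChAd3-EBO-Z recipients is a different clarification and not part of this point. SAP 6.3.1 already presents results by the treatment given at Day 0.

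**What to change.** In SAP 14.1.2, state that each overall coefficient is an age-stratified Spearman (ranks taken within age stratum) or a Spearman partial on age. Show it with a confidence interval beside the three stratum-specific coefficients that protocol 11.9 already requires. The partial version removes the small residual that three broad strata leave. If dose differs between strata, the stratified version also takes out that difference.

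In SAP 7.5, add that the three age strata are planned presentations under protocol 11.9 and are not covered by the statement on subgroups.

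The cost is a sentence or two in each section. Age and stratum are already recorded, so no new data are needed, and stratifying uses two degrees of freedom.
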